6.2.6 Postoperative pain and side effects

Pain at rest, pain after coughing, nausea and tiredness will be registered at 4h, 10h, 24h and 48 h after administration of test drug in the CMT pilot trial..

A numeric rating scale ranging from 0-10 is used (0 = no discomfort, 10 = maximal discomfort imaginable). The variables will be treated as continuous in the statistical analyses.

6.2.7 Consumption of analgesics

Postoperative pain treatment protocol includes oral paracetamol 1 g and ibuprofen 400 mg 4 times daily and IV morphine administered by a patient controlled analgesia pump (PCA). In the CMT pain trial, overall postoperative morphine consumption in mg will be measured, as well as morphine consumption in the time periods 0-4h, 4-10h, 10-24h and 24-48h after test drug administration.

A continuous variable measured in mg.

6.2.8 QOL forms detecting level of anxiety, depression and pain catastrophizing trait

Prior to the operation the patients will be asked to fill in QOL forms detecting level of anxiety, depression and pain catastrophizing trait. Only in the CMT pain trial.

6.2.8.1 Modified three simple questions

A numeric rating scale ranging from 0-100 is used to rate anxiety, anticipated level of pain, need for analgesics and coping with motherhood (0 = not at all, 100 = to an extreme degree). The variables will be treated as continuous in the statistical analyses.

6.2.8.2 Pain Catastrophizing Scale (PCS)

PCS consists of 13 questions scored as follows.

- 0 = not at all
- 1 = to a slight degree
- 2 = to a moderate degree
- 3 = to a great degree
- 4 = all the time

The overall score is achieved by summarizing the scores of the 13 questions. Results from the PCS will range from 0-52. The variable will be treated as continuous in the statistical analyses.

A PCS score of ≥ 30 is considered to be associated with clinical relevance. Reported level of PCS ≥ 30 will be reported as a binary variable (PCS $< 30 = 0$, and PCS $\geq 30 = 1$).

6.2.8.3 Hopkins Symtom CheckList (HSCL-25)

HSCL-25 consists of 25 questions measuring level of anxiety and depression. Each question is scored as follows.

- 1 = Not at all
- 2 = A little bit
- 3 = Quite a bit
- 4 = Extremely

The value for HSCL-25 is obtained by calculating the mean score of the 25 questions. The variable will be reported as a continuous variable.

HSCL-25 of ≥ 1.75 is considered clinically relevant, and will be reported as a binary variable (HSCL-25 $< 1.75 = 0$, HSCL-25 $\geq 1.75 = 1$).

6.2.9 ECG changes

In the CMT pilot trial, the patients will be attached to a digital Holter monitor (Medilog AR4, Schiller) during the C-section to evaluate ECG changes during the first 10 minutes following administration of test drug.

The following parameters will be registered:

- Occurrence of ischemic episode (ST-segment depression of $\geq 0.1\text{mV}$). Registered as a binary variable (no ischemic episode = 0, one/more ischemic episodes = 1)
- Duration of ischemic episode. Continuous variable measured in seconds.

- Degree of ST-segment depression from baseline. Continuous variable measured in mV.
- Beat to beat analysis of QT time corrected according to Framingham. Continuous variable measured in msec.
- Occurrence of arrhythmia. Registered as a binary variable (no episodes of arrhythmia = 0, one/more episodes of arrhythmia = 1)

6.2.8 Time consumption

Time consumption from time of delivery until end of surgery and from time of delivery to time of discharge from postoperative ward unit.

A continuous variable measured in minutes.

6.3 Summary of endpoints (TABLE)

OUTCOME	ENDPOINT	TYPE
Primary	Troponin I level	Continuous
Other myocardial markers	Troponin T level	Continuous
	CK level	Continuous
	CK-MB level	Continuous
	NT-proBNP level	Continuous
Other blood analyses	Hemoglobin level	Continuous
	Sodium level	Continuous
	Biobank analyses	Continuous
Uterine tone	Uterine tone	Continuous
	Time till rescue, min	Continuous
Blood loss	Calculated blood loss, ml	Continuous
Perioperative side effects	Severity of side effects	Ordered categorical
	Treatment of side effects	Binary
Postoperative pain and side eff.	Pain at rest	Continuous
	Pain after coughing	Continuous
	Nausea	Continuous
	Tiredness	Continuous
Consumption of analgetics	Morphine consumption, mg	Continuous
QOL forms	Modified three simple questions	Continuous
	PCS	Continuous
	PCS \geq 30	Binary
	HSCL-25	Continuous
	HSCL-25 \geq 1.75	Binary
ECG changes	Occurrence ischemic episode	Binary
	Duration ischemic episode, sec	Continuous
	ST-segment depression, mV	Continuous
	Prolonged QTc interval	Binary
	Beat to beat analyses QTc interval	Continuous
	Occurrence of arrhythmia	Binary
Time consumption	Time consumption, min	Continuous

7.0 STATISTICAL METHODOLOGY

7.1 Sample size determination

7.1.1 CMT pilot trial

The predefined main outcome variable in this double blinded randomized controlled study is group differences in changes over time in high sensitive troponin I levels. This is the first clinical study comparing these outcome measures and calculation of statistical power and group size estimations are not possible. After all data from 40 patients (1:1 group size) have been collected, a blinded analysis based on these study data will be performed by a medical statistician, who will get access to outcome measures and information about treatment allocation, but not the actual treatment. Unblinding will be performed when all analyses have been completed.

7.1.2 CMT2 trial

Based on preliminary results of the CMT pilot trial, the largest difference in plasma troponin I concentration was found at 10 hours, with a mean±standard deviation change from baseline of 0.41 ± 0.79 ng/L in the carbetocin group versus a mean change of 1.78 ± 4.48 in the oxytocin group. The sample size calculation was based on 80% power to detect a between-group difference in change from baseline to 10 hours of 1.37, to be analysed using a two-sample T-test with adjustments for unequal variances. With a significance level of 5%, we will need to include 178 patients (89 in each treatment group) in the CMT2 trial. To adjust for loss of information from missing values and patient drop outs, 240 women will be enrolled. The drop-out rate after enrolment is expected to be low as the duration of the study is short.

7.2 Randomization

After inclusion, patients will be randomized to one of two study arms. The randomization will be performed immediately before study start. The person responsible for preparing the study drug will be unblinded and not otherwise involved in patient treatment. Research personnel involved in patient treatment, data collection and analysis will not receive information about actual treatment allocation until all data has been collected and analyses have been completed. Randomization will be performed by a researcher not involved in the data collection. The randomization responsible will decide block size and if variable block size will be used.

7.3 Blinding

All study participants will be blinded to the treatment allocation with the exception of the person responsible for preparing the study drug and the person generating the randomization list. These persons will not be the same as the one responsible for analysis of the trial data. Blinding of study drug will be secured by using standard 5 ml syringes marked with date and randomization number according to study protocol.

7.4 Statistical methods

7.4.1 Primary and secondary analyses

The primary analysis will be a modified intention to treat analysis of the primary outcome (highly sensitive troponin I) on the full analysis set. We will initially perform a blinded analysis of the primary outcome.

Secondary analyses will be:

1. A per protocol analysis on the primary outcome (troponin I) on the per protocol analysis set
2. Modified intention to treat analyses of all secondary outcomes on the full analysis set
3. Sensitivity analyses to examine the impact of missing data (Section 7.4.5)

7.4.2 Repeated-measures continuous outcomes

The primary endpoint and all other continuous endpoints, including baseline and ≥ 1 follow-up measurements, will be analysed with linear regression models, with the follow-up measurement defined as the dependent variable and treatment group and baseline measurement defined as independent variables. Based on the fitted models, we will estimate treatment group differences in changes from baseline with 95% confidence intervals (CIs), together with a p-value for the null hypothesis of no treatment group difference. We expect at least some degree of skewness in the primary and some of the secondary endpoints, and maybe also in the residuals from the linear regression models. The amount of skewness will be assessed with histograms and descriptive statistics, such as mean, median, variance, and the skewness index. In cases where the distribution of the residuals deviates markedly from the normal distribution, or when the endpoints themselves are too skewed to use means as measures of central tendency, we will use median regression models instead of linear regression models, thus analysing between-group differences in median changes from baseline instead of mean changes from baseline. Standard errors and CIs in the median regression models will be obtained via bootstrapping with 100 replications.

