4.2 Statistical decision rule

The primary and all secondary outcomes will be analysed with two-sided tests and confidence intervals and a statistical significance level of 5%.

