7.4.3 Continuous outcomes measured at single time points

Continuous outcome variables measured at single time points will be analysed with two-sample t-tests (and 95% confidence intervals for the differences between means), with adjustment for unequal variances (the Welch U test). In situations where the distribution of the variable is difficult to assess or deemed to be highly skewed, median regression models will be used instead of t-tests to test and estimate differences in medians.

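### The primary linear model in SAP 7.4.2 names no standard error that allows for unequal variances, although the sample size in SAP 7.1.2 assumes them

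*SAP*

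**What the plan says.** SAP 7.1.2 reports pilot changes at 10 hours of "0.41 ± 0.79 ng/L in the carbetocin group" and "a mean change of 1.78 ± 4.48 in the oxytocin group". It sizes CMT2 on a comparison "to be analysed using a two-sample T-test with adjustments for unequal variances" and concludes that "we will need to include 178 patients (89 in each treatment group) in the CMT2 trial". The enrolment target is then raised to 240.

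SAP 7.4.3 carries the same precaution into outcomes measured once, which are compared by t-test "with adjustment for unequal variances (the Welch U test").

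SAP 7.4.2, which governs the primary endpoint, fits a linear regression with treatment and baseline as covariates and adds: "Based on the fitted models, we will estimate treatment group differences in changes from baseline with 95% confidence intervals (CIs"). It names no type of standard error for this model and plans no comparison of the variances of the two arms. It specifies bootstrap errors only for median regression, which replaces the linear model if residuals are markedly non-normal or the endpoint is too skewed. Protocol 10.3 names ANCOVA or a mixed model and is also silent on the variance structure.

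Allocation is 1:1 (SAP 2.1). The full analysis set keeps only women who received study drug (SAP 5.2), and the primary analysis is complete-case (SAP 7.4.5).

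**The concern.** The SAP allows for unequal variances in the sample size and in single-time outcomes. It does not do so for the primary endpoint, the one place where its own pilot data show a large difference in spread. An ordinary linear regression estimates one residual variance for both arms. With equal arms this gives the right standard error for the treatment difference. With unequal arms it does not: if the high-variance arm (oxytocin in the pilot) is the smaller one, the interval is too narrow; if it is the larger one, the interval is too wide.

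Exact equality is unlikely. SAP 5.2 expects some women to leave before study drug because of early labour, rescheduling or general anaesthesia, and complete-case analysis can remove more. What is at stake is the calibration of the primary p-value and confidence interval for the split that actually occurs. A second stake is that the standard error would be chosen after the arm sizes are known.

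**Working it through.** **Inputs.** SDs of change 0.79 (carbetocin) and 4.48 (oxytocin), from SAP 7.1.2; variances 0.6241 and 20.0704, ratio 32.2. The calculation was "based on 80% power to detect a between-group difference in change from baseline to 10 hours of 1.37". SAP 4.2 has outcomes "analysed with two-sided tests and confidence intervals and a statistical significance level of 5" per cent. Arm sizes below are assumptions, as is using SDs of raw change as residual SDs after baseline adjustment.

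**The plan's own figure.** At 89 per arm, the unequal-variance SE is √((0.6241 + 20.0704)/89) = 0.482, the noncentrality is 1.37/0.482 = 2.84 and the Satterthwaite df are 93.5. Power is 80.3%, and 89 is the smallest number per arm that reaches 80%. The stated 178 is reproduced exactly.

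**Pooled against true standard error.** For arm sizes n_c (carbetocin) and n_o (oxytocin):

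- pooled variance s² = [(n_c − 1)(0.6241) + (n_o − 1)(20.0704)]/(n_c + n_o − 2)
- pooled SE = √[s²(1/n_c + 1/n_o)]
- true SE = √(0.6241/n_c + 20.0704/n_o)
- type I error ≈ 2·P(Z > t_crit × pooled SE/true SE), with t_crit = 1.9735 on 176 df

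Example, 96 carbetocin and 82 oxytocin: s² = (95 × 0.6241 + 81 × 20.0704)/176 = 9.574. The pooled SE is 0.465 and the true SE 0.501, ratio 0.928. Then 1.9735 × 0.928 = 1.832, and the type I error is 6.7%.

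| Carbetocin / oxytocin | SE ratio | Type I error |
|---|---|---|
| 89 / 89 | 1.000 | 4.8% |
| 92 / 86 | 0.969 | 5.6% |
| 86 / 92 | 1.032 | 4.2% |
| 93 / 85 | 0.958 | 5.9% |
| 85 / 93 | 1.043 | 4.0% |
| 96 / 82 | 0.928 | 6.7% |
| 82 / 96 | 1.077 | 3.4% |

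Using Satterthwaite df in place of the normal reference adds 0.2 to 0.4 points to each row and leaves the pattern unchanged.

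**How likely such gaps are.** The SAP gives no loss rate. Assume 120 per arm and that the whole margin, 240 − 178 = 62, exits regardless of arm. The number leaving one arm has SD √(62 × ½ × ½ × 178/239) = 3.4, so the gap between arms has SD 6.8. A gap of 8 or more then has probability about 30%, and 14 or more about 5.5%. With 20 exits the gap SD falls to 4.3.

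**Average over splits.** Weighting the type I error by the probability of each split gives 4.9% for 20, 40 or 62 exits (5.1–5.2% with Satterthwaite df). The share of splits with an error between 4% and 6% is about 98%, 86–91% and 76% respectively.

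**With a robust standard error.** In a simulated ANCOVA with normal errors (20,000 trials per setting), HC3 standard errors gave 4.9–5.2% at all eight splits tried, from 89/89 to 130/110 and 110/130.

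**The case against.** Several points on the other side stand.

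- A reader might infer that the SAP prescribes a common-variance standard error. It does not. It is silent, and pooling is the default when no other estimator is named. The authors did write the unequal-variance adjustment out in 7.1.2 and 7.4.3, which makes the default the natural reading of 7.4.2, but the gap is one of specification.
- A reader might also infer that the trial's type I error is inflated. The documents do not support that. Exits before drug happen under blinding, so they should not depend on arm, and the two directions cancel on average. What remains is accuracy for the realised split, usually about 1 point either way.
- Large imbalances are easy to quote but hard to reach. A split of 120/100 from 240 randomised equally needs all 20 exits in one arm, a probability of about 8 in 10 million.
- Losing 62 women is the extreme of the planned margin. SAP 7.1.2 expects few drop-outs and 7.4.5 little missing data. SAP 7.2 places randomisation immediately before study start, which would limit later exits, although Protocol 10.2 ties it to first registration in the electronic CRF.
- The linear model may not be used. SAP 7.4.2 expects skewness, and a mean change of 1.78 with SD 4.48 suggests it. If median regression with bootstrap errors takes over, this point falls away.
- The SDs come from a 40-woman pilot and describe raw change; residual SDs by arm are not given.

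What these points do not answer is the case where the linear model is kept. The switch depends on non-normality or skewness, with no stated threshold, and not on unequal variances. Linear regression is still the default.

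**Conclusion.** The point holds as a minor one. SAP 7.4.2 leaves the variance estimator of the primary linear model unspecified, and the default does not match the unequal-variance basis of the sample size. If the linear model is kept and the analysed arms differ, the confidence interval and p-value are off by about 1 point of type I error in ordinary cases, and by just under 2 points at a gap of 14. The direction depends on which arm is smaller. At equal arms there is no material error.

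These sizes rest on the pilot SDs serving as residual SDs, normal errors, about 178 women analysed and exits unrelated to arm. The documents do not support saying that the primary interval is wrong as planned, or that the trial's validity is at risk.

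**What to change.** In SAP 7.4.2, add that the linear model for the primary endpoint uses heteroscedasticity-consistent (HC3) standard errors for its confidence interval and p-value. This brings it into line with 7.1.2 and 7.4.3. The model, the estimate and the median-regression rule stay as they are.

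The cost is one phrase and one software option. The 178 already assumes unequal variances and does not change, and nothing material is lost at equal arms. The documents show no variance difference for haemoglobin, sodium or the other outcomes under 7.4.2, so extending the phrase to them is optional. It should be settled before treatment allocation is revealed.

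### The fallback median regression, which may become the primary analysis, rests on 100 bootstrap replications, few enough for resampling noise to decide a borderline result at 5%

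*SAP*

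**What the plan says.** For outcomes with a baseline and at least one follow-up value, including troponin I, SAP 7.4.2 makes linear regression adjusted for baseline the default. It then warns: "We expect at least some degree of skewness in the primary and some of the secondary endpoints". If residuals are clearly non-normal, or the endpoint is too skewed for means to be useful, "we will use median regression models instead of linear regression models". For those models, "Standard errors and CIs in the median regression models will be obtained via bootstrapping with 100 replications".

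The same section promises a 95% confidence interval and a p-value. SAP 4.2 sets the decision rule: "two-sided tests and confidence intervals and a statistical significance level of 5" per cent.

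Neither document states a random seed, the type of bootstrap interval, or how the median-regression p-value is obtained. SAP 7.4.3 also uses median regression, for skewed outcomes measured once, and gives no bootstrap detail. SAP 7.4.6 names only the software. Protocol 10.3 mentions neither median regression nor bootstrapping.

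**The concern.** A bootstrap standard error is itself an estimate, and its own random error depends on the number of replications. With 100, that error is large enough that two analysts running the stated method on the same locked data with different seeds can report different p-values. When the p-value is near 0.05, they can reach different verdicts.

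This would matter little for a method kept for minor outcomes. Here the plan itself expects skewness in the primary endpoint. The pilot changes in SAP 7.1.2 (0.41 ± 0.79 and 1.78 ± 4.48 ng/L) have standard deviations larger than their means. Changes can be negative, so this does not prove skewness, but it fits the SAP's expectation. The primary conclusion could therefore rest on these 100 replications.

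**Working it through.** **Inputs.** From the SAP: B = 100 replications (7.4.2), a two-sided 5% level (4.2), and 89 per arm for 80% power (7.1.2). Assumed: a normal-approximation (Wald) interval and p-value based on the bootstrap standard error, and 80% power for the median analysis. SAP 7.1.2 powers a difference in means, "to be analysed using a two-sample T-test with adjustments for unequal variances", and neither document gives power for medians.

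**The plan's own figure.** With a difference of 1.37 and SDs of 0.79 and 4.48, the noncentral t with Satterthwaite degrees of freedom gives power 0.798 at 88 per arm and 0.803 at 89. The stated 178 therefore reproduces and is not affected by this point.

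**Error in the standard error.** Its coefficient of variation across seeds is about 1/√(2(B−1)).
- B = 100: 1/√198 = 7.1%
- B = 1,000: 1/√1,998 = 2.2%
- B = 2,000: 1/√3,998 = 1.6%

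**Chance of landing on the wrong side of 5%.** Call the p-value with unlimited replications the limiting p, and let z be its two-sided normal quantile. (B−1)·SE_boot²/SE² is approximately chi-square with B−1 degrees of freedom, so P(reported p < 0.05) = F((z/1.96)²·(B−1)), where F is that chi-square distribution function.
- Limiting p = 0.04, B = 100: z = 2.054, argument 108.7, F = 0.763. Wrong side: 23.7%.
- Limiting p = 0.06, B = 100: z = 1.881, argument 91.2, F = 0.300. Wrong side: 30.0%.

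| Limiting p | B = 100 | B = 1,000 | B = 2,000 |
|---|---|---|---|
| 0.02 | 0.5% | 0 | 0 |
| 0.03 | 6.3% | 0 | 0 |
| 0.04 | 23.7% | 1.6% | 0.1% |
| 0.06 | 30.0% | 3.6% | 0.5% |
| 0.08 | 6.9% | 0 | 0 |
| 0.10 | 1.1% | 0 | 0 |

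(0 means below 0.05%.)

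**Averaged over possible trials.** These figures integrate the wrong-side probability over z ~ N(0,1) for the null and z ~ N(2.80,1) for 80% power (1.96 + 0.84 = 2.80).

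| | B = 100 | B = 1,000 | B = 2,000 |
|---|---|---|---|
| Verdict changed, null | 1.3% | 0.4% | 0.3% |
| Verdict changed, 80% power | 3.1% | 1.0% | 0.7% |

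Type I error is 5.28% at B = 100 and 5.01% at B = 2,000; power is 79.9% and 80.0%. The limiting p lies between 0.03 and 0.08 in 5.0% of trials under the null and 11.7% at 80% power.

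**Simulation check.** Median regression of follow-up on group and baseline was run on one assumed skewed data set with 89 per arm, drawing sets of 100 from 6,000 bootstrap replicates. The standard error varied by 6.9%, and the wrong-side rates were 23% at 0.04 and 29% at 0.06, in line with the formula.

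**If a percentile interval is used instead.** With a normal bootstrap distribution, the wrong-side rate at B = 100 depends on how the 2.5th percentile of 100 values is defined.

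| Quantile rule, B = 100 | 0.04 | 0.06 |
|---|---|---|
| Linear interpolation | 23% | 52% |
| Empirical distribution function | 32% | 42% |
| (B+1)p | 46% | 28% |

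At B = 2,000 the range over rules is 5–7% at 0.04 and 8–10% at 0.06.

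**The case against.** The strongest reply is that the effect is small and doubly conditional. The switch to median regression must happen, and the limiting p must then be near 0.05. The 24% and 30% apply only at exactly 0.04 and 0.06; the averaged figures are 1.3% and 3.1%, and the second rests on an assumed power. This stands, and it sets the weight of the point.

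It is also fair to say that the link to the p-value is inferred. The sentence covers standard errors and intervals only. Because it names standard errors first, an SE-based p-value is the natural reading, and the percentile interval the less likely one. The missing p-value rule is part of the same gap.

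Two stronger readings are tempting and are not supported.

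- A reader might infer that the seed or interval could be chosen after seeing a result. SAP 7.4.1 says "We will initially perform a blinded analysis of the primary outcome", and in the pilot (7.1.1) the blinded analysis was done by a statistician "who will get access to outcome measures and information about treatment allocation, but not the actual treatment". That coded-group arrangement is described only for the pilot. For CMT2 the SAP does not say what the blinded analysis uses, and 7.2 says that those treating patients, collecting data and analysing them "will not receive information about actual treatment allocation until all data has been collected and analyses have been completed". Nothing suggests that several seeds would be tried. Fixing the seed first is good practice, not a response to a demonstrated weakness.
- A reader might quote one percentile-interval figure, such as 52% at 0.06, as the size of the problem. At 100 replications that figure ranges from 28% to 52% with the quantile rule, and the SAP names neither the interval nor the rule.

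**Conclusion.** The point holds as a minor one. The defect is the stated count of 100; the unstated seed, interval and p-value rule alone would only be missing detail. If the fallback is used for troponin I and its p-value comes from the bootstrap standard error, about 7% noise in that standard error changes the verdict at 5% in roughly 1.3% of trials under the null and 3.1% at an assumed 80% power. Results with a limiting p of 0.02 or below, or 0.10 or above, are essentially unaffected. The treatment estimate is not biased.

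The documents do not support saying that the switch will occur, since the SAP expects only some skewness and keeps linear regression as the default. An optional change is the right weight, and it is worth making because it is nearly free.

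**What to change.** Replace the last sentence of SAP 7.4.2 with, for example: *In the median regression models, standard errors will come from 2,000 bootstrap replications; 95% CIs and p-values will use the normal approximation with that standard error. The random seed, [integer], is fixed before the first analysis of the primary outcome.* In SAP 7.4.3, add that median regression follows the same specification.

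The number 2,000 and the normal approximation are reasonable choices, not the only correct ones. At least 2,000 is advised, with the exact number written down. Another interval can be named; a percentile interval needs a higher count for the same stability, and its quantile rule should be stated. The interval must be named whatever the count. In the one simulated skewed data set, scaled to a normal-based limiting p of 0.04, normal and percentile intervals disagreed on excluding zero in 61% of runs at 100 replications and in nearly all runs at 2,000. A fixed seed makes the result reproducible, but only more replications reduce the noise.

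The cost is one sentence, a cross-reference and a little computing time. Sample size, data collection and the estimate itself do not change.
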